#### 9.1.2. Exclusion criteria

- Patient not completing at least 1 cycle of InO therapy
- Patient on InO in combination with chemotherapy

Following local legislation, informed consent won't be signed by the patients since this is a retrospective study and they are not getting enrolled in a prospective clinical trial. All data points mentioned in the inclusion criteria should be available which are necessary to analyze protocol endpoints for the selected patient cohort who has undergone the full treatment of the drug in question. Ethics Committee approval of study protocol will be taken to access medical records.

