#### 9.7. Limitations of the research methods

- The medical records may not be available for each & every data points provided in the CRF, from the aspect of the clinician or the patient.
- Patients may be lost to follow-up due to the occurrence of AEs, lack of efficacy or other reasons.
- This could be due to censoring events, that is, information on time to outcome event may not available for all study participants. Patient/s in such cases will be marked as "censored" when such information on time to event is not available due to loss to follow-up or non-occurrence of outcome events before the end of the study.
- For such patients (censored because of lost to follow-up due to the occurrence of AEs, lack of efficacy or other reasons), the use of Kaplan-Meier curves will be obtained as estimates of median OS, RFS and time to CR/Cri taking into account patients' attrition.
- The interpretation of data collected retrospectively will be dependent on the completeness and quality of the medical records and the reliability of the abstraction of data from the medical records. However, Source data verification (SDV) will be employed to identify and correct abstraction errors.

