# 4 ANALYSIS SETS/POPULATIONS

The population of interest will be the Relapsed/Refractory B Cell Acute lymphoblastic leukemia adult patients in India who had initiated and completed at least one cycle of InO monotherapy between Feb'2017 and Feb'2022 and CD22 positive.

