# 4.1 FULL ANALYSIS SET

The restrospective available record of all Relapsed/Refractory B Cell Acute lymphoblastic leukemia adult patients satisfying specified inclusion and exclusion criteria will be the full analysis set.

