# **Exclusion criteria**

- *Patient not completing at least 1 cycle of InO therapy*
- Patient on InO in combination with chemotherapy

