# 5 ENDPOINTS AND COVARIATES

Following local legislation, informed consent won't be signed by the patients since this is a retrospective study and they are not getting enrolled in a prospective clinical trial. All data points mentioned in the inclusion criteria should be available which are necessary to analyze protocol endpoints for the selected patient cohort who has undergone the full treatment of the drug in question. Ethics committee approval of study protocol will be taken to access medical records.

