# 6 HANDLING OF MISSING VALUES

Owing to the descriptive nature of the study, analysis will be on available data only. No imputation of missing data will be implemented.

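### An undefined full-treatment and data-availability sentence after the exclusion criteria conflicts with the 1-cycle population and may make entry depend on events after the index date

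*Protocol*

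**What the plan says.** The free text under Protocol 9.1.2 states: "All data points mentioned in the inclusion criteria should be available which are necessary to analyze protocol endpoints". The same sentence goes on to describe the patients concerned as those with full treatment; the data meant are those "necessary to analyze protocol endpoints for the selected patient cohort who has undergone the full treatment of the drug in question". SAP section 5 repeats it, again "for the selected patient cohort who has undergone the full treatment of the drug in question".

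The listed rules are narrower. The only exclusions are combination with chemotherapy and "Patient not completing at least 1 cycle of InO therapy". SAP section 4 describes the population as adults who "had initiated and completed at least one cycle of InO monotherapy". SAP 4.1 says that the records of all patients "satisfying specified inclusion and exclusion criteria will be the full analysis set".

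Other parts of the plan expect gaps and early stops:
- Protocol 9.7 warns that "The medical records may not be available for each & every data points provided in the CRF". It names adverse events and lack of efficacy among the reasons for loss to follow-up, and it censors those patients.
- SAP section 6 says that "analysis will be on available data only", without imputation.
- Protocol section 3 counts stopping InO because of general decline as an RFS event.
- Protocol section 11 counts patients whose InO was interrupted for VOD/SOS.

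Neither document defines full treatment. The nearest term is in Protocol section 3, where the CR/CRi denominator is patients completing InO, meaning those with a recorded discontinuation date. The SAP does not carry that definition; its Appendix A1.2 gives no further endpoint definitions.

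**The concern.** The sentence sits in the eligibility section and describes the selected cohort, so a site abstracting charts may apply it as a further entry rule. A patient who stopped after one or two cycles for progression or toxicity meets the listed criteria but may not count as fully treated. A patient lost to follow-up meets the listed criteria but may lack endpoint data.

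Both properties are settled after the index date and may be related to outcome. Selecting on them can shift the CR/CRi proportion, which is the primary endpoint, and also MRD, survival, RFS, dose-modification and toxicity summaries. The selection would happen before a CRF is filled in. Protocol 9.6.1 describes checking, for a sample, that included patients exist in the records. Neither document describes a screening log or a count of eligible patients left out, so the analysis data would neither show the loss nor allow it to be corrected.

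**Working it through.** There is no figure in the plan to reproduce. The sample size rests on availability, and no response rate is targeted. The check is a comparison of texts, followed by an illustration.

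**Step 1: what each reading does.**

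| Reading of the sentence | 1-cycle criterion and full analysis set | Censoring and available-data rules |
|---|---|---|
| Only eligibility data are needed; full treatment just means that treatment is over | No material conflict | No conflict |
| Full treatment means a recorded discontinuation date (borrowed from Protocol section 3) | Conflict largely goes: recorded treatment failures stay in. A patient with no recorded date, for example after loss to follow-up, would still drop out | No direct conflict |
| Full treatment means the whole intended course | Conflict: early stoppers pass the listed criteria but fail this one | RFS events from stopping early would be lost |
| Endpoint data must be available | Conflict: neither rule has this condition | Conflict: patients the plan would censor or analyse on available data might not enter |

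The wording does not settle which reading applies. It points to data in the inclusion criteria, which are age, diagnosis, InO start date, CD22 status and, for Ph+ patients, TKI failure. It also calls these necessary to analyse the endpoints, yet they cannot supply response, MRD or survival.

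**Step 2: how far the primary proportion could move.** Let p be the CR/CRi rate among all patients with at least 1 cycle, f the share of non-responders left out, and g the share of responders left out.

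Observed rate = p(1 − g) / [p(1 − g) + (1 − p)(1 − f)]

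Inputs: p = 40% is the top of the historical CR range in Protocol section 7, and p = 81% is the InO response rate there from the cited phase 3 trial. p = 60% is an assumed middle value. The documents give neither f nor g, so all values of both are assumptions.

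For p = 60%:
- f = 25%, g = 0: 0.60 / (0.60 + 0.40 × 0.75) = 0.60/0.90 = 66.7%
- f = 75%, g = 0: 0.60 / (0.60 + 0.40 × 0.25) = 0.60/0.70 = 85.7%
- f = 0, g = 25%: 0.45 / (0.45 + 0.40) = 52.9%
- f = 0, g = 50%: 0.30 / (0.30 + 0.40) = 42.9%

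| True rate | f = 25% | f = 50% | f = 75% | g = 25% | g = 50% |
|---|---|---|---|---|---|
| 40% | 47.1% | 57.1% | 72.7% | 33.3% | 25.0% |
| 60% | 66.7% | 75.0% | 85.7% | 52.9% | 42.9% |
| 81% | 85.0% | 89.5% | 94.5% | 76.2% | 68.1% |

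If f = g, the terms cancel and the rate does not change.

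**Step 3: in patients.** The administrative change letter sets the size at 32. Suppose 19 respond: 19/32 = 59.4% (exact 95% CI 40.6% to 76.3%).
- Leave out 6 non-responders: 19/26 = 73.1% (52.2% to 88.4%).
- Leave out 6 responders instead: 13/26 = 50.0%.
- Leave out 8 early stoppers, of whom 2 responded: 17/24 = 70.8%.

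**The case against.** The strongest defence is that this is loose prose and not a criterion. It stands between a consent statement and an ethics statement, it is not in either list, and in the SAP it is outside section 4.1. Its verb is should. Its data clause names the inclusion criteria, so read literally it asks for little more than proof of eligibility. If full treatment takes the meaning that Protocol section 3 gives to completing InO, patients who stopped for progression or toxicity stay in whenever the stop date is recorded. The last eligible InO start was February 2022 and the revised start of data collection was 13 February 2023, about a year later, so most patients had probably stopped by then. The RFS definition and the VOD/SOS counts show that the authors expected early stoppers in the cohort.

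Much of this stands. It rules out presenting the sentence as a plain rule that excludes anyone with missing endpoint data.

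It does not make the sentence safe. The section 3 term is a different phrase attached to one denominator, and a site would have to guess that it applies. Because eligibility data alone cannot analyse the endpoints, the broader reading is natural.

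A reader might also infer that the sentence selects patients on treatment success and so inflates response. The documents do not support that as fact. Protocol 9.7 makes an upward bias plausible by naming adverse events and lack of efficacy as reasons for loss. But Protocol section 7 presents remission followed by transplant as the curative route, and 41% of InO patients in the cited phase 3 trial went on to HSCT. If responders who stop for transplant count as not fully treated, the bias runs downward.

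**Conclusion.** The point holds as an unresolved contradiction about who enters the cohort. Read as an entry condition, the sentence cannot be squared with the 1-cycle criterion, the SAP population or the full analysis set. If it covers endpoint data, it also clashes with the censoring and available-data rules. Sites working from the same text could build different cohorts, and entry may depend on treatment completion and record completeness after the index date.

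The size and direction of any bias cannot be established from the documents. The shifts above depend wholly on assumed losses. They show only that, with 32 patients, leaving out six could move the primary proportion by roughly 9 to 14 points in either direction (59.4% to 50.0% or to 73.1%). Nothing in the documents shows that any site has left patients out. The repair is still warranted, because the sentence bears on the primary proportion and its effect could not be corrected later from CRF data.

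**What to change.** Delete the sentence from Protocol 9.1.2 and SAP section 5. In its place state, for example: *Only the data needed to confirm the listed inclusion and exclusion criteria are required for entry. All eligible patients with at least 1 completed cycle are included, whatever their later treatment course, length of follow-up or completeness of endpoint data.*

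Then:
- Align the CR/CRi denominator in Protocol section 3 with that set, so that a missing discontinuation date does not remove a patient from the primary proportion.
- Ask each site whether anyone was left out under the present wording, and restore those patients.
- Report the number of patients excluded, with reasons.

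This restores the population that the listed criteria and SAP 4.1 already define, and sets no clinical rule. It costs one replaced sentence in each document, one edited definition and a short clarification to sites, plus chart abstraction for any restored patients. The downside is more missing fields, which the plan already expects, and possibly less favourable rates.

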### 9.1.3. Primary endpoint

Complete remission or complete remission with incomplete hematological recovery following treatment with InO, by the number of salvage therapies  $(0, 1, \ge 2)$  received before InO initiation.

#### 9.1.4. Secondary endpoints

- MRD Negativity following initiation of Ino
- Number of cycles of InO needed to attain CR/CRi
- DOR
- Dosage pattern: InO doses, dose modifications, and the number of cycles of treatment;
- Concomitant medications
- Rate of transplant (No of patients who proceeded to transplant)
- Survival rate at 6 months & 12 months (transplanted patients & non transplanted patients, in both who achieved CR/CRi and MRD negativity)
- Cause of death
- Relapse-free-survival; in all patients and patients with or without follow-up HSCT.
- Rate of VOD (Total, during study treatment and post HSCT, if any patient underwent HSCT) in transplanted & non transplanted patients.
- Occurrence of Grade 3/4 treatment-related adverse events in lung/cardiac/kidney/liver etc following InO initiation; in all patients and patients with or without follow-up HSCT & hematological toxicities
- CR/CRi in EMD/LBL

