# **3. KEY DEFINITIONS**

Index date: The date of initiation of the first cycle of InO.

**Baseline period**: Period from 6 months before index date to the index date. The closest observation recorded during the baseline period and closest to index date will be used as baseline data (when more than one observations are available).

**CR/CRi rate**: Number of patients who achieve complete remission/complete remission with incomplete hematologic recovery (CR/Cri) divided by the total number of patients completing treatment with InO (defined as patients with a recorded date of discontinuation of InO).

**Complete remission (CR)**: is defined as 5% bone marrow blasts, no evidence of disease in the bone marrow, and recovery of peripheral blood count (platelet count of >  $100 \times 109/L$  and absolute neutrophil count of >  $1 \times 109/L$ ).

**CR with incomplete count recovery (CRi)**: is defined as 5% bone marrow blasts and no evidence of disease in the bone marrow, but with incomplete recovery of peripheral blood count. Minimal residual disease (MRD) will be assessed at each participating institution by multicolor flow cytometry.

**MRD negativity r**ate: Proportion of patients in whom minimal residual disease (MRD)-negative status is observed, among patients in whom MRD negativity status has been assessed, at any time until the end of treatment with InO (defined as the date of recorded discontinuation of InO). OS: Time from index date to death.

**RFS:** Time from index date to the earliest date of the following events: death, progressive disease (including objective progression, relapse from CR/CRi, treatment discontinuation due to global deterioration of health status), or the start of new induction therapy or posttherapy haematopoietic stem cell transplantation (HSCT) without achieving CR/CRi.

**EMD**: Extramedullary disease is the presence of leukemic cell aggregates in the form of solid tumor outside that of bone marrow.i

LBL: lymphoblastic lymphoma, is a clonal hematopoietic stem cell disorder of B or T cell originii

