#### PFIZER CONFIDENTIAL

CT24-WI-GL02-RF02 4.0 Non-Interventional Study Protocol Template For Secondary Data Collection Study 01-Jun-2022 Page 12 of 24 vincristine, corticosteroids and an anthracycline with allogeneic stem cell transplantation for eligible candidates.x

The advent of moAb targeting CD22 (InO) and CD19 (blinatumomab), have dramatically improved the outcome of adults with R/R B cell ALL. These have shown significant survival benefits against standard therapies and expanded the armamentarium of ALL.xi

InO is an anti-CD22 moAb conjugated to the cytotoxic antibiotic calicheamicin. Based on promising phase I/II data, InO was compared to standard salvage chemotherapy in Phase 3 multicenter trial (INO-VATE) of 218 adult patients with CD22+ B cell ALL. The overall response and MRD negativity rates among responders were significantly higher with InO compared with chemotherapy (81% versus 29%, p < 0.001, and 78% versus 28%, p < 0.001, respectively). More patients who received InO were able to undergo HSCT (41% versus 11%; p < 0.001). The median remission duration and progression-free survival were significantly longer with InO (4.6 versus 3.1 months; p = 0.03, and 5.0 versus 1.8 months; p < 0.001, respectively). The median OS was 7.7 versus 6.7 months (p = 0.04). This was later confirmed with longer follow-up on 326 patients showing 2-year OS rates of 23% versus 10% (p = 0.01) in favor of InO [24]. Predictors for better survival included achievement of CR, MRD negativity, and consolidative HSCT. Patients who achieved MRD negativity derived more benefits regardless of the number of prior therapies.xii

InO is an ADC comprising of a moAb targeting CD22,xiii a cell surface antigen expressed on approximately 90% of B-cell malignancies,xiv linked to a cytotoxic agent.

CD22 is an important modulator of B-cell lymphocyte function and survival,xv and is expressed on mature B-cells, which may allow for targeted delivery of the cytotoxic agent.xvi

When InO binds to the CD22 antigen on malignant B-cells, it is absorbed into the cell, at which point the cytotoxic agent calicheamicin is released to destroy the cell.xvii

Adding an ADC targeting CD22, such as InO, to existing treatments options, may provide additional anti-tumor activity.xviii

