## 9.1. Study design /Setting

The study is classified as a Non-interventional study (NIS) secondary data collection- unstructured review with sites/investigators.

R/R B-cell ALL patients who are 18 years old at the time of InO initiation and those who received the drug outside of clinical trials will be evaluated.

Data will be collected retrospectively from patients hospital medical records (paper-based ) by members of the direct care team (investigators). We intend to have 7- 10 sites across India using InO monotherapy including patients with both private purchase and compassionate use to reach a cohort of approximately 55. If needed, more sites will be enrolled to meet the target cohort. Data will be reviewed and analyzed from all the sites.

Medical records will be reviewed to collect demographic, patient-related, disease-related, and clinical outcome data. These patients will be evaluated for response (CR/CRi), MRD status, duration of remission (DOR), Dosage patterns, Rate of transplant, Overall survival in all patients including Survival rate at 6 months and 12 months in transplanted patients & non transplanted patients, Relapse free survival (RFS), Rate of VOD (Total, during study treatment and post HSCT if any patient underwent HSCT), safety/tolerability, Other adverse effects (including hematological toxicities and raised liver enzymes), No of cycles to achieve MRD negativity in responders & CR/CRi in EMD/LBL.

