#### This PACL makes the following changes:

	izer		
3	6. MILESTONES	Change in Milestones- Planned Date	Start of data collection - 13 February 2023 End of data collection - 05 July 2023 Final Study report - 10 October 2023
4	9. RESEARCH METHODS 9.3 Study size	Sample size changed to 32 subjects	Sample size is changed to 32 subjects
5	11. MANAGEMENT AND REPORTING OF ADVERSE EVENTS/ADVERSE REACTIONS 12. SAFETY REPORTING	To clarify the adverse event reporting requirements for structured and unstructured data components. Also, to correct the inconsistency with the protocol template language.	The last 2 paragraphs of Section 11 should be moved to the beginning of Section 12, Adding a subheading "12.1 Structured Data Analysis", under which the 2 paragraphs are pasted and revised. In addition, add a second sub- heading "12.2 Human Review of Unstructured Data" above the original content of Section 12.

In the event that this protocol requires substantial changes that apply globally to all sites in the future or regulatory authorities request that these changes be incorporated into an updated protocol, the administrative changes described in this letter will be incorporated into the amended protocol.

Please inform your institutional review board/ ethics committee of these changes, as required.

Sincerely, [name]

cc: NI study master file

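### Survival and RFS run from the first InO cycle but are to be split by later HSCT status with no landmark, so the HSCT split is distorted even with no transplant effect

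*Protocol*

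**What the plan says.** **Clock.** Protocol section 3 defines OS as "Time from index date to death", the index date being the start of the first InO cycle. RFS has the same origin. SAP 5.1 also measures death and relapse from the start of therapy. One RFS event is "the start of new induction therapy or posttherapy haematopoietic stem cell transplantation (HSCT) without achieving CR/CRi".

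**Survival by HSCT.** Protocol 9.1.4 and SAP section 5 list "Survival rate at 6 months & 12 months (transplanted patients & non transplanted patients, in both who achieved CR/CRi and MRD negativity". Protocol 9.1 words it as "Overall survival in all patients including Survival rate at 6 months and 12 months in transplanted patients & non transplanted patients", and SAP 2.1 is similar. SAP 2.2 drops the time points. SAP 7.1, 7.2, 7.2.2 and section 8 give no 6- or 12-month survival rate and no OS analysis by HSCT: output 12 and figure 3 are not split by it.

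**RFS by HSCT.** SAP 7.2 plans restricted RFS with 95% CI for all patients and by follow-up HSCT, if data permit. This is output 13 in SAP 7.2.2 and section 8.

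**Safeguards.** There is no landmark, time-dependent state or clock reset, and SAP Appendices 1 and 2 add nothing. Protocol 9.7 deals with record quality, loss to follow-up and censoring, stating that "the use of Kaplan-Meier curves will be obtained as estimates of median OS, RFS and time to CR/Cri".

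**The concern.** A patient must live to the transplant date to be counted as transplanted. A patient who dies after cycle 1 but before any transplant is counted as non-transplanted. Time before HSCT is therefore guaranteed survival in one group and at risk in the other (immortal-time bias). Kaplan-Meier estimation deals with censoring, not with grouping on a future event.

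For RFS a second force acts. A transplant without CR/CRi is itself an event, so those patients fail on the day they enter the HSCT group. The two forces can partly cancel or reverse the gap.

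At stake is how two secondary displays will be read. The rows will stand side by side, and Protocol section 7 already names consolidative HSCT as a predictor of better survival, so a gap produced by the grouping could pass for confirmation.

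**Working it through.** The plan has no power or precision figure to reproduce. The check asks how large a gap appears when HSCT has no effect.

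**Inputs from the documents (proxies from the phase 3 trial quoted in Protocol section 7).** Median OS 7.7 months; median PFS 5.0 months, standing in for RFS; share transplanted p = 0.41 ("More patients who received InO were able to undergo HSCT (41% versus 11"%). N = 32 (administrative change letter, item 4: "Sample size is changed to 32 subjects").

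**Assumed, not in the documents.** HSCT month h; an early period d without deaths (for RFS, without events), motivated by the exclusion "Patient not completing at least 1 cycle of InO therapy"; responder median OS of 12 to 18 months; share q transplanted without CR/CRi; a 12-month RFS horizon, since the SAP names none.

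**1. Survival, whole cohort.** S(t) = exp(−ln2·(t−d)/m) for t > d, and 1 before.
- Transplanted: S(t)/S(h).
- Non-transplanted: [S(t) − p·S(t)/S(h)]/(1−p).

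With d = 1, m = 7.7, h = 3: S(3) = 0.8352, S(6) = 0.6376, S(12) = 0.3715.
- 6 months: 0.6376/0.8352 = 76.3% against (0.6376 − 0.41×0.7633)/0.59 = 55.0%. Gap 21.3 points.
- 12 months: 44.5% against 32.1%. Gap 12.4 points.

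| Setting | 6-month gap | 12-month gap |
|---|---|---|
| d = 1, h = 3 | 21.3 | 12.4 |
| d = 2, h = 3 | 11.1 | 6.5 |
| d = 1, h = 1 to 5 | 0 to 46.8 | 0 to 27.3 |
| d = 1, h = 3, p = 0.20 to 0.50 | 15.7 to 25.2 | 9.2 to 14.7 |
| d = 1, h = 3, overall median held at 7.7 (m = 6.7) | 23.2 | 12.5 |

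**2. Survival, responders only** (same formula, h = 3, p = 0.41, m = 12 to 18). With d = 1: 11.2 to 15.5 points at 6 months and 8.9 to 11.0 at 12. With d = 2: 5.7 to 8.0 and 4.5 to 5.7.

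**3. At the planned size** (simulation, 32 patients, d = 1, HSCT spread over months 2 to 4). The 6-month split favours HSCT in 89% of cohorts, with a mean gap of 21 points. With 26 responders (0.81 × 32, the quoted response rate) it does so in 77 to 82%, or 65 to 69% with d = 2.

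**4. RFS split from index** (simulation, d = 1, median parameter 5.0). HSCT-minus-other gap in 12-month restricted mean, in months:

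| HSCT timing | q = 0 | q = 20% | q = 50% |
|---|---|---|---|
| month 2 | +1.3 | +0.2 | −1.4 |
| month 3 | +2.5 | +1.5 | 0.0 |
| months 2 to 4 | +2.5 | +1.5 | −0.1 |

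**5. Does a landmark remove it?** For survival, yes: with HSCT over months 2 to 4 and a 4-month landmark, the mean 12-month gap is −0.15 point. For RFS, a landmark on event-free status alone gives 0.0 only if every transplant precedes it. With HSCT over months 2 to 6 and a 4-month landmark, the false gap is about +0.4 month (q = 20%) and +0.9 to +1.0 (q = 50%). With HSCT over months 2 to 4 and a 3-month landmark it is about +0.4 and +0.9; the latter is worse than the from-index −0.1. The reason is that a transplant without CR/CRi after the landmark is classed as non-HSCT and then fails in that group. A patient event-free and in CR/CRi at the landmark cannot later meet that event clause, so this restriction closes the route by definition.

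**The case against.** **The study is descriptive.** This stands in part. SAP section 3 states no hypothesis, no HSCT test is named, and SAP 7.2 limits extrapolation and makes interpretation qualitative. A reader might infer that the plan will test HSCT groups and produce false positives; the documents do not say that. However, SAP 7.2 accepts that features are compared numerically, and Protocol 9.5 allows outcomes to be compared across clinical factors at p<0.05. A distorted estimate stays distorted without a test.

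**The SAP does not specify the survival split.** This stands. For 6- and 12-month survival the certain defect is an endpoint without a method; the bias follows if someone fills the gap with a from-index split. Output 13 is planned as such, though only if data permit.

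**The size rests on assumptions.** This stands. Neither HSCT timing nor cycle length is given. Protocol 9.1.2 also speaks of patients who had the full treatment, which could remove more early deaths; with none before month 2 the gaps roughly halve. For RFS, completing cycle 1 does not rule out an early event.

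**RFS must favour HSCT too.** A reader might infer this from the survival result. The RFS definition does not support it, as the table under step 4 shows.

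**Conclusion.** The concern holds and should be fixed. As written, output 13 groups patients by an event after the clock starts, and a 6/12-month survival display built the same way would favour HSCT with no transplant effect unless no deaths precede transplant.

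With HSCT assumed at month 3, the illustrative survival gaps are about 21 and 12 points (no deaths in month 1), about 11 and 6.5 (none before month 2), or about 5 to 16 if the endpoint means responders only. These are not estimates for this cohort: they rest on the quoted trial's 7.7 months and 41% and on assumed HSCT timing. The RFS distortion has no fixed sign.

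The documents do not support extending the point further. The primary endpoint and whole-cohort OS and RFS from index are unaffected.

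**What to change.** In SAP 7.2 and output 13, and in any 6/12-month survival display by HSCT, replace the split by eventual HSCT status with one landmark earlier than 6 months, fixed before data review.

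- **Survival:** patients alive at the landmark, grouped by HSCT status at that time. State whether all patients or only CR/CRi and MRD-negative patients are meant; if the latter, take response status at the landmark too.
- **RFS:** patients event-free and in CR/CRi at the landmark, grouped in the same way. State the restriction horizon and what counts as follow-up HSCT.
- **Reporting:** 95% CIs, no test, and the numbers excluded. Report survival from the HSCT date separately.
- **Limitations:** selection for HSCT remains, and the split is not evidence of a transplant effect.
- **Fallback:** if HSCT dates or numbers do not allow a landmark, show the from-index split only with an explicit immortal-time caveat and no comparison.

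Keep whole-cohort OS and RFS from index as planned.

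**Cost.** SAP wording and a few lines of code; HSCT dates are needed, and the documents do not show that the CRF captures them. Groups shrink. At a 4-month landmark 32 × exp(−ln2×3/7.7) ≈ 24 are alive, about 12 of them transplanted if HSCT falls in months 2 to 4 and 6 to 7 if in months 2 to 6. For RFS at most 32 × exp(−ln2×3/5) ≈ 21 are event-free, falling to about 15 (6 transplanted) if half of the transplants in months 2 to 4 occur without CR/CRi; the CR/CRi restriction lowers this further. After a 4-month landmark the 6-month rate covers only 2 months, so the 12-month rate carries most of the information.
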